APPENDIX 2. RESPONSE ASSESSMENT FOR NEURO-ONCOLOGY (RANO) CRITERIA FOR TIME POINT RESPONSES

1. Definitions and Baseline Classification

Baseline is defined as the screening assessment performed immediately prior to commencement of any study treatment.

The following definitions are to be applied:

Measurable Lesions

Measurable lesions are enhancing lesions that can be measured bi-dimensionally with clearly defined margins by computed tomography (CT) or magnetic resonance imaging (MRI).

Minimal Diameter:

Lesions must have two perpendicular diameters of at least 10 mm, visible on two or more axial slices that are preferably, at most, 5 mm apart with 0-mm skip.

Note: After baseline, target lesions that become smaller than the minimum requirement for measurement or become no longer amenable to bi-dimensional measurement are to be recorded at the default value of 5 mm for each diameter below 5 mm until the lesion disappears (recorded as 0 × 0 mm).

Multicentric Lesions

Multicentric lesions are lesions where there is normal intervening brain tissue between the two (or more) lesions. If there is no normal brain tissue between these two (or more) lesions, they will be considered the same lesion.

For multicentric lesions that are discrete foci of enhancement, no more than 3 separately enhancing lesions should be identified and the sum of the product of the diameters (SPD) measured.

Non-Measurable Lesions

All other lesions that do not meet the criteria for measurable disease as defined, as well as all non-enhancing and other truly non-measurable lesions, are considered non-measurable.

A non-measurable lesion will include foci of enhancement that are less than the specified smallest diameter, non-enhancing lesions seen on T2-weighted or fluid attenuated inversion recovery (FLAIR) images, hemorrhagic or predominantly cystic or necrotic lesions, and leptomeningeal tumor. Hemorrhagic lesions often have intrinsic T1-weighted hyperintensity that could be

misinterpreted as enhancing tumor, and for this reason, the pre-contrast T1-weighted image must be examined to exclude baseline or interval sub-acute hemorrhage.

At baseline, lesions are to be identified as follows:

- a. **Target lesions:** Up to 5 measurable lesions, each at least 10 × 10 mm, representative of the patient's disease
- b. **Non-target lesions:** All other lesions, including all non-measurable lesions and any measurable lesions not chosen as Target lesions

2. Post-Treatment Evaluation

At each evaluation, a time point response is to be determined for target lesions, non-target lesions, and new lesion. The RANO criteria and associated conventions for each post-treatment time point assessment are provided in [Appendix Table 5](#). Overall time point response is derived as described in [Appendix Table 6](#).

Unless progression is observed, overall response can only be determined when all lesions are assessed.

3. Confirmation

Confirmation assessments for overall time point responses of complete response (CR) and partial response (PR) are to be performed no less than 4 but no more than 8 weeks after the initial time point at which a response is seen.

4. Best Response

Best response, incorporating confirmation requirements, will be derived from the series of time point responses and need not be considered when assigning response at each time point.

Appendix Table 5: RANO Criteria For Time Point Responses (TPR)

Prerequisite

If the daily dose of glucocorticoids is not the same for each of the 5 days preceding the current MRI, target or non-target lesion TPR is to be designated NE (not evaluable). To avoid this designation, MRI should be delayed until these glucocorticoid criteria can be met, and every effort should be made to ensure the MRI is performed on schedule while meeting these criteria.

Target Enhancing Lesion (T1/post-contrast) Time Point Response (TPR)

Target Lesion TPR	Criteria
NA	No Target enhancing lesions identified at baseline
PD	
≥25% increase in sum of the products of perpendicular diameters (SPD) of the target enhancing lesions compared to the prior MRI (since and including baseline) with the nadir SPD for the target enhancing lesions and on a stable or increasing dose of glucocorticoids.
 
(If the glucocorticoid dose is neither stable nor increased, a Target Lesion TPR of NE is to be assigned.)

NE	≥ 1 target enhancing lesions were not assessed unless progression is observed
CR	
Disappearance of all enhancing target lesion(s); and,
 
No glucocorticoids (other than a physiologic replacement dose of a maximum of 1.2 mg dexamethasone equivalent dose per day) taken for the 5 days immediately preceding the date of the current MRI.
 
(If glucocorticoid dose is greater than a physiologic replacement dose, a Target lesion TPR of PR is to be assigned.)

PR	
≥50% decrease in the SPD of all target enhancing lesions compared to the baseline MRI; and glucocorticoids stable or decreased,
 
(If the glucocorticoid dose is neither stable nor decreased, a Target Lesion TPR of SD is to be assigned.)

SD	Target lesion TPR not qualify for PD, NE, CR or PR

CR, complete response; MRI, magnetic resonance imaging; NA, not applicable; NE, not evaluable, PD = progressive disease, PR, partial response; SD, stable disease; TPR, time point response.

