Appendix Table 5: RANO Criteria For Time Point Responses (TPR) (Continued)

Non-Target Enhancing Lesion (T1/post-contrast) Time Point Response (TPR)

Non-Target Lesion TPR		Criteria
NA		No Non-Target enhancing lesions identified at baseline
PD	MRI: Non-target enhancing (T1/post-contrast)	Unequivocal progression (not due to co-morbid events) of one more non-target enhancing lesions compared to the prior MRI (since and including baseline) with the nadir for the non-target enhancing lesions; and on stable or increasing dose of glucocorticoids. (If the glucocorticoid dose is neither stable nor increased, a Non-Target Lesion TPR of NE is to be assigned.)
NE	≥ 1 non-target enhancing	lesions were not assessed unless progression is observed
CR	MRI: Non-target enhancing (T1/post-contrast)	Disappearance of all enhancing non-target lesion(s); and, No glucocorticoids (other than a physiologic replacement dose of a maximum of 1.2 mg dexamethasone equivalent dose per day) taken for the 5 days immediately preceding the date of the current MRI. (If glucocorticoid dose is greater than a physiologic replacement dose, a Non-Target lesion TPR of PR is to be assigned.)
SD	Non-Target TPR does not qualify for PD, NE, CR or PR	

CR, complete response; MRI, magnetic resonance imaging; NA, not applicable; NE, not evaluable; PD; progressive disease, PR, partial response; SD, stable disease; TPR, time point response.

Time Point Response (TPR) (New Lesions)

New Lesion TPR	Criteria
Yes	
 One or more new lesions (enhancing (T1/post-contrast) or non-enhancing (T1/pre-contrast or T2/FLAIR)) compared to the baseline MRI, regardless of glucocorticoid dose Significant increase on T2/FLAIR (including mass effects) not due to co-morbid events (eg, radiation therapy, demyelination, ischemic injury, infection, seizures, postoperative changes, or other treatment effects based upon a review of all prior T2/FLAIR images) compared to the T2/FLAIR image at the prior time point (since and including baseline) with the nadir SPD for the target enhancing lesions; and on stable or increasing dose of glucocorticoids steroids. 
If #2 is met and glucocorticoid dose is neither stable nor increased, a time point response of NE is to be assigned.

NE	Absence of new lesions was not established or T2/FLAIR not assessed.
No	No new lesions compared to baseline MRI and no significant increase on T2/FLAIR (including mass effects)

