Appendix Table 6: Overall Time Point Response

Criterion	CR	PR	SD	PD
T1 gadolinium enhancing disease	None	≥ 50% ↓	< 50% ↓ but < 25% ↑	≥ 25% ↑
T2/Flair	Stable or ↓	Stable or ↓	Stable or ↓	↑*
New lesion	None	None	None	Present*
Corticosteroids	None	Stable or ↓	Stable or ↓	NA [†]
Clinical Status	Stable or ↑	Stable or ↑	Stable or ↑	↓*
Requirement for response	All	All	All	Any*

CR, Complete Response; FLAIR, Fluid-Attenuated Inversion Recovery; NA, Not Applicable; PD, Progressive Disease; PR, Partial Response; SD, Stable Disease

* Progression occurs when this criterion is present

[†] Increase in corticosteroids alone will not be taken into account in determining progression in the absence of persistent clinical deterioration

Reference: [Wen PY, Macdonald DR, Reardon DA et al. Updated response assessment criteria for high-grade gliomas: response assessment in neuro-oncology working group. J. Clin. Oncol. 2010;28 \(11\):1963-72.](#)

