6.4.2 Secondary Efficacy Endpoints

Disease Control Rate (DCR – for arm C)

DCR is defined as the proportion of patients with best overall response of CR, PR or SD per RANO criteria. CR or PR will be confirmed by a subsequent tumor assessment at least four weeks apart. DCR will be performed in similar fashion as described in primary endpoint modified DCR on Efficacy Analysis Set.

Objective Response Rate (ORR – for arm A&B)

ORR for arm A&B will be performed for Efficacy Analysis Set in similar fashion as in primary endpoint for arm C.

Progression-Free Survival (PFS)

PFS is defined as the time from the first dose date to disease progression per RANO criteria or death, whichever occurs first. PFS analysis will be performed for all arms using Safety Analysis Set.

PFS censoring rule will follow FDA *Guidance for Industry, Clinical Trial Endpoints for Approval of Cancer drugs and Biologics* (2007). The censoring rules are described in Table 1. If a patient meets the criteria for more than 1 censoring rule, PFS will be censored at the earliest censoring date.

Table 1 Censoring Rules for Analysis of Progression-Free Survival

Censoring Categories	Date of Progression or Censoring	Outcome
Progression documented on scheduled visit or between scheduled visits	Date of first PD assessment	Progressed
Death before first tumor assessment	Date of death	Progressed
Death between scheduled adequate assessment visits	Date of death	Progressed
No baseline or postbaseline tumor assessments	Date of the first dose	Censored
No PD or death at the time of data cut-off or withdrawal from study	Date of last adequate radiologic tumor assessment prior to or on date of data cut-off or withdrawal from study	Censored

New anticancer treatment started	Date of last adequate radiologic tumor assessment prior to or on date of new anticancer treatment	Censored
Death or PD immediately after two or more missed visits	Date of last adequate radiologic tumor assessment before missed tumor assessments	Censored

CR = complete response, PD = progressive disease, PR = partial response, SD = stable disease
Adequate tumor assessment is a radiologic assessment of CR, PR, SD, non-CR/non-PD or PD as determined by investigators.

Duration of Response (DOR)

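### A scan whose only progression finding is growth on a reduced steroid dose is NE under Appendix Table 5 but PD under Appendix Table 6, so PFS and DOR depend on which table is followed

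*Protocol*

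**What the plan says.** **Protocol Appendix 2, Appendix Table 5** gives component responses.

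- Target lesions are PD on a "≥25% increase in sum of the products of perpendicular diameters (SPD) of the target enhancing lesions" from the nadir MRI, "and on a stable or increasing dose of glucocorticoids". For any other dose, "If the glucocorticoid dose is neither stable nor increased, a Target Lesion TPR of NE is to be assigned".
- Non-target enhancing lesions: "If the glucocorticoid dose is neither stable nor increased, a Non-Target Lesion TPR of NE is to be assigned".
- A significant T2/FLAIR increase is item 2 of the new-lesion block: "If #2 is met and glucocorticoid dose is neither stable nor increased, a time point response of NE is to be assigned".

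**Appendix 2, Post-Treatment Evaluation** then states: "Overall time point response is derived as described in" Appendix Table 6.

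**Appendix Table 6** lists a T1 increase of at least 25% and a T2/FLAIR increase in its PD column, enters NA for corticosteroids there, and requires any one criterion. Its steroid footnote reads "Increase in corticosteroids alone will not be taken into account in determining progression" unless there is persistent clinical deterioration. That covers a rising dose and is silent on a falling one. The columns are CR, PR, SD and PD; there is none for NE.

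**SAP Section 6.4.2, Table 1** dates a PFS event at the first PD assessment and censors at the last adequate assessment. Its footnote states: "Adequate tumor assessment is a radiologic assessment of CR, PR, SD, non-CR/non-PD or PD as determined by investigators". NE is not in that list. DOR uses the same censoring rules. SAP Section 6.4 says that no independent reads will be requested, so the investigator's call stands.

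**The concern.** One finding leads to two response calls. An investigator who applies the Table 5 steroid condition records NE; one who reads the overall response from Table 6 records PD. The SAP has no rule to settle it, and no central read will harmonise the choice.

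The calls lead to different PFS data. Read as PD, the patient has an event on the scan date. Read as NE, the scan is neither an event nor an adequate assessment. If progression is called at a later scan, the event moves to that date. If new anticancer treatment starts first, PFS is censored at the last adequate scan before the growth. That censoring is prompted by suspected progression, so it is informative. Both routes lengthen PFS. In a single-arm study no control group shares the same distortion.

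**Working it through.** **Step 1. Which scans are affected.** Take a scan whose only finding is target growth of at least 25%, and apply each table.

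| Steroid dose against the reference scan | Table 5 | Table 6 |
|---|---|---|
| Stable | PD | PD |
| Increased | PD | PD |
| Decreased | NE | PD |

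The tables part only for a decreased dose. Three conditions narrow the group:

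- A new lesion is called regardless of steroid dose, and clinical decline is PD in Table 6, so neither may be present.
- The dose must have been constant over the 5 days before the MRI; otherwise the Table 5 prerequisite already gives NE.
- The dose must be lower than at the reference scan.

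The T2/FLAIR case is the clearest. Table 5 assigns NE there as a time point response, and Table 6 stars the T2/FLAIR increase as progression. In the text as read, the T1 cell of at least 25% carries no star. No other Table 6 column fits such a scan, however, because even SD needs growth below 25%.

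**Step 2. Effect on one patient's PFS.** Inputs: 1 month = 30.4375 days (SAP Section 6.2.2), so 6 months = 6 × 30.4375 = 182.6 days; MRI every 8 weeks (56 days); repeat imaging 4 to 8 weeks after first radiographic progression (Protocol Section 8.3.1). Visit windows are ignored.

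- Delay of 8 weeks: 56 / 30.4375 = 1.84 months.
- Arm A, nominal scans on days 71–78, 127–134 and 183–190. NE on day 127–134 (4.2–4.4 months) with PD 8 weeks later puts the event at 6.0–6.2 months, past the six-month landmark. With PD 4 weeks later (day 155–162, 5.1–5.3 months) it does not cross.
- Arm C, nominal scans on days 57, 113, 169 and 225. NE on day 169 (5.6 months) moves to day 197 (6.5 months) or day 225 (7.4 months). Both cross.

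**Step 3. Effect on PFS-6m.** The documents give no frequency, so these inputs are assumptions: exponential PFS with a 4-month median (121.75 days), scans every 56 days from Day 1, and a share f of first growth scans affected, with f = 10% or 20%.

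- Per-interval survival: s = 0.5^(56/121.75) = 0.7270. Three scans fall before day 182.6 (days 56, 112 and 168).
- All called PD: s³ = 0.3843, or 38.4%.
- Called NE, event delayed: only events due on day 168 leave the window, and their mass is s² − s³ = 0.5285 − 0.3843 = 0.1443. PFS-6m = 0.3843 + f × 0.1443 = 39.9% (f = 10%) or 41.3% (f = 20%). A 4-week delay gives the same figures on this grid, because 168 + 28 = 196 days is also beyond 182.6.
- Called NE, all such patients censored at the prior scan: each Kaplan–Meier factor becomes s / (1 − f(1 − s)). For f = 10%, (0.7270/0.9727)³ = 0.4175. For f = 20%, (0.7270/0.9454)³ = 0.4547.

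A simulation of 400,000 patients gave 38.4%; 39.8% and 41.3% with delay; and 41.7% and 45.4% with censoring.

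**Step 4. Modified DCR.** SAP Section 6.2.1 counts only CR, PR or SD at the EOT visit, so PD and NE are both non-responses and the numerator is the same. For Arms A and B, the Efficacy Analysis Set in SAP Section 6.1 asks for a tumor assessment at baseline and at End of Treatment. It does not ask for an adequate one.

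**The case against.** The best defence is that the tables work in sequence: Table 5 sets component responses with their conventions, Table 6 combines them, and all that is missing is an NE row. This is a fair account of how the gap may have arisen, but it does not close it. If Table 5 goes first, Table 6 has no column for the result. If Table 6 governs, the three Table 5 steroid rules have no effect. The T2/FLAIR rule is also worded as a time point response, so the difference is not only one of levels.

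It can also be said that stable has no stated reference point. If it means constant over the 5 days before the MRI, every scan that passes the prerequisite is PD in both tables. The NE clauses would then have nothing left to do, which is hard to square with stating them three times.

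Other parts of the defence stand. The group is narrow. Eight weeks is the upper end of the delay. The 10% to 20% share is not from the documents, and the censoring figures need every such patient to switch therapy before a PD call. The shifts are also small against sampling error: around 39%, the 95% half-width is 1.96 × √(0.39 × 0.61/40) = 15 points with 40 patients and 17 points with 30, ignoring censoring.

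A reader might infer that the Arm A primary endpoint is at risk, because an NE scan at EOT could remove a patient from the denominator. The documents do not support this. The adequacy requirement appears only in the PFS censoring table, and an MRI read as NE is still a tumor assessment under SAP Section 6.1.

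**Conclusion.** The conflict is real and confined to one situation: growth of at least 25% or a significant T2/FLAIR increase as the only progression finding, at a steroid dose lower than at the reference scan. PFS and DOR, both secondary and descriptive, depend on which table the investigator follows, and the NE reading always makes PFS longer.

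Under the stated assumptions PFS-6m rises by about 1 to 3 points if events are delayed, and by at most about 3 to 7 points if every affected patient is censored. The true effect cannot be computed, because the share of affected scans is unknown. Modified DCR is not shown to change. The point merits correction because two response rules disagree and the remedy is cheap, not because the likely shift is large.

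**What to change.** 1. **Protocol Appendix 2.** State once whether and how the steroid condition applies to PD, with the reference point for a stable dose, and say how a component-level NE enters the overall time point response. Which reading is clinically right is for the sponsor and investigators to decide; the need is for both tables to say the same thing.
2. **SAP Section 6.4.2.** State how such scans are handled in the main PFS and DOR analyses. Keep the Table 1 rule that censors at new anticancer treatment. Dating an event at the growth scan because new therapy followed would contradict that rule.
3. **Sensitivity analysis.** Report PFS and DOR under the other reading (PD on the scan date versus NE), identifying the scans from recorded measurements and steroid doses rather than from the investigator's label.

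The cost is an appendix clarification, a sentence in the SAP and one extra run. Enrolment is reported as complete at 116, so the clarification may come after many reads, which is why the sensitivity analysis should rest on recorded data. PFS may come out slightly shorter.

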Appendix Table 5: RANO Criteria For Time Point Responses (TPR) (Continued)

Non-Target Enhancing Lesion (T1/post-contrast) Time Point Response (TPR)

Non-Target Lesion TPR		Criteria
NA		No Non-Target enhancing lesions identified at baseline
PD	MRI: Non-target enhancing (T1/post-contrast)	Unequivocal progression (not due to co-morbid events) of one more non-target enhancing lesions compared to the prior MRI (since and including baseline) with the nadir for the non-target enhancing lesions; and on stable or increasing dose of glucocorticoids. (If the glucocorticoid dose is neither stable nor increased, a Non-Target Lesion TPR of NE is to be assigned.)
NE	≥ 1 non-target enhancing	lesions were not assessed unless progression is observed
CR	MRI: Non-target enhancing (T1/post-contrast)	Disappearance of all enhancing non-target lesion(s); and, No glucocorticoids (other than a physiologic replacement dose of a maximum of 1.2 mg dexamethasone equivalent dose per day) taken for the 5 days immediately preceding the date of the current MRI. (If glucocorticoid dose is greater than a physiologic replacement dose, a Non-Target lesion TPR of PR is to be assigned.)
SD	Non-Target TPR does not qualify for PD, NE, CR or PR	

CR, complete response; MRI, magnetic resonance imaging; NA, not applicable; NE, not evaluable; PD; progressive disease, PR, partial response; SD, stable disease; TPR, time point response.

Time Point Response (TPR) (New Lesions)

New Lesion TPR	Criteria
Yes	
 One or more new lesions (enhancing (T1/post-contrast) or non-enhancing (T1/pre-contrast or T2/FLAIR)) compared to the baseline MRI, regardless of glucocorticoid dose Significant increase on T2/FLAIR (including mass effects) not due to co-morbid events (eg, radiation therapy, demyelination, ischemic injury, infection, seizures, postoperative changes, or other treatment effects based upon a review of all prior T2/FLAIR images) compared to the T2/FLAIR image at the prior time point (since and including baseline) with the nadir SPD for the target enhancing lesions; and on stable or increasing dose of glucocorticoids steroids. 
If #2 is met and glucocorticoid dose is neither stable nor increased, a time point response of NE is to be assigned.

NE	Absence of new lesions was not established or T2/FLAIR not assessed.
No	No new lesions compared to baseline MRI and no significant increase on T2/FLAIR (including mass effects)

MRI, magnetic resonance imaging; FLAIR, Fluid-Attenuated Inversion Recovery; NE, not evaluable, TPR, time point response.

Appendix Table 6: Overall Time Point Response

Criterion	CR	PR	SD	PD
T1 gadolinium enhancing disease	None	≥ 50% ↓	< 50% ↓ but < 25% ↑	≥ 25% ↑
T2/Flair	Stable or ↓	Stable or ↓	Stable or ↓	↑*
New lesion	None	None	None	Present*
Corticosteroids	None	Stable or ↓	Stable or ↓	NA [†]
Clinical Status	Stable or ↑	Stable or ↑	Stable or ↑	↓*
Requirement for response	All	All	All	Any*

CR, Complete Response; FLAIR, Fluid-Attenuated Inversion Recovery; NA, Not Applicable; PD, Progressive Disease; PR, Partial Response; SD, Stable Disease

* Progression occurs when this criterion is present

[†] Increase in corticosteroids alone will not be taken into account in determining progression in the absence of persistent clinical deterioration

Reference: [Wen PY, Macdonald DR, Reardon DA et al. Updated response assessment criteria for high-grade gliomas: response assessment in neuro-oncology working group. J. Clin. Oncol. 2010;28 \(11\):1963-72.](#)

APPENDIX 3. EASTERN COOPERATIVE ONCOLOGY GROUP (ECOG) PERFORMANCE STATUS

Grade	Description
0	Fully active, able to carry on all pre-disease performance without restriction
1	Restricted in physically strenuous activity but ambulatory and able to carry out work of a light or sedentary nature, eg, light house work, office work
2	Ambulatory and capable of all self-care but unable to carry out any work activities. Up and about more than 50% of waking hours
3	Capable of only limited self-care, confined to bed or chair more than 50% of waking hours
4	Completely disabled. Cannot carry on any self-care. Totally confined to bed or chair
5	Dead
As published by (Oken et al, 1982). Eastern Cooperative Oncology Group, Robert Comis M.D., Group Chair.	

